7. STATISTICAL METHODS AND DETERMINATION OF SAMPLE SIZE

7.1 STATISTICAL DESIGN - MODEL

This is a randomised, double blind, multi-centre, placebo-controlled, parallel group, 26 week study to assess the efficacy, safety, tolerability, and PK of once daily oral doses of empagliflozin 2.5 mg, 10 mg and 25 mg compared to placebo in patients with T1DM as adjunctive to insulin therapy.

The superiority of the 3 doses of empagliflozin will be tested against placebo. A Bonferroni adjustment will first correct for the parallel testing of the 2 higher doses (empagliflozin 25 mg and 10 mg) in order to maintain a type I error rate of 0.05. Each of these 2 doses will therefore be tested at the level of α =0.025 (two-sided).

Following the efficacy analysis (on-treatment data only) of the primary endpoint, change from baseline in HbA_{1c} after 26 weeks, for the 2 higher doses, an effectiveness analysis (on-and off-treatment data) will be performed in a hierarchical manner. If the null hypothesis is rejected for both the efficacy and effectiveness analysis the error rate will be unequally split and transferred between the testing of the lowest dose empagliflozin 2.5 mg (with an allocated alpha weight of 1/5) and the testing of key secondary endpoints (with an allocated alpha weight of 4/5) in a gatekeeping strategy. If the null-hypothesis of "equal HbA_{1c} change after 26 weeks between placebo and empagliflozin 2.5 mg" can be rejected using ontreatment data only, alpha of this test will be equally split and added to the alpha level for the test of the key secondary endpoints of the two higher doses.

Superiority of empagliflozin 10 mg versus placebo in key secondary endpoints will be sequentially tested with an unequal alpha split. The same approach will be followed to test superiority of empagliflozin 25 mg versus placebo on these endpoints.

See Section 7.2 for further details on the endpoint testing strategy.

With regard to efficacy and safety endpoints, the term "baseline" refers to the last observed measurement prior to administration of any randomised study medication, the 4 week period prior to randomisation for the rate of hypoglycaemia and the run-in period from Visit 5 to Visit 6 for the mean daily insulin requirement.

Patients who prematurely discontinue trial medication will continue to attend all visits and be followed up until the end of the trial when possible.

The randomisation will be stratified by the Visit 5 eGFR value (< $60 \text{ mL/min/1.73 m}^2$ versus $\geq 60 \text{ mL/min/1.73 m}^2$), the Visit 5 HbA_{1c} value (< 8.5% versus $\geq 8.5\%$), by the patients' pre-existing insulin therapy (MDI versus CSII), and by the patient's participation in the CGM substudy (CGM participation versus non-CGM participation). If necessary, and depending upon global distribution, entry of patients into a particular HbA_{1c} stratum may be capped.

Page 75 of 122

Proprietary confidential information © 2016 Boehringer Ingelheim International GmbH or one or more of its affiliated companies

7.2 NULL AND ALTERNATIVE HYPOTHESES

The following testing procedure will be used to evaluate the superiority for the primary endpoint for empagliflozin 25 and 10 mg doses against placebo at the level of $\alpha = 0.025$. The overall probability of type I error is therefore maintained at $\alpha = 0.05$ (two-sided).

The superiority of treatment with empagliflozin to placebo will be tested for HbA_{1c} change from baseline at Week 26, via the pairwise comparison of the two higher empagliflozin doses against placebo, at $\alpha = 0.025$ level. Both doses will be tested in parallel on the Full Analysis Set (FAS) for the efficacy analysis and on the modified Intention-to-Treat (mITT) set for the effectiveness analysis; see Section 7.3 for the analysis set definitions. Both analyses will test the same null hypothesis:

H_{0,0,1}: Mean change from baseline in HbA_{1c} (%) after 26 weeks in the empagliflozin 10 mg group = Mean change from baseline in HbA_{1c} (%) after 26 weeks in the placebo group

 $H_{0,0,2}$: Mean change from baseline in HbA_{1c} (%) after 26 weeks in the empagliflozin 25 mg group = Mean change from baseline in HbA_{1c} (%) after 26 weeks in the placebo group

Following testing of the null hypotheses $H_{0.0.1}$ and $H_{0.0.2}$ for both efficacy and effectiveness for HbA_{1c}, within each dose group (empagliflozin 10 and 25 mg) the remaining alpha will be unequally split for testing the superiority of empagliflozin 2.5 mg to placebo on the primary endpoint and for testing the superiority of the key secondary endpoints for the higher doses as detailed below.

One-fifth of the remaining alpha will be used for testing the superiority of empagliflozin 2.5 mg to placebo on the primary endpoint. The test will be done twosided. The null hypothesis is as follows:

 $H_{0.0.3}$: Mean change from baseline in HbA_{1c} (%) after 26 weeks in the empagliflozin 2.5 mg group= Mean change from baseline in HbA_{1c} (%) after 26 weeks in the placebo group

Depending on the success of the testing of $H_{0,0,1}$ and $H_{0,0,2}$, $H_{0,0,3}$ will be tested at the following alpha level $\alpha_{0,3}$:

- If either $H_{0,0,1}$ or $H_{0,0,2}$ is rejected at 0.025 level, then $\alpha_{0.3} = 1/5 \times 0.025 = 0.005$.
- If $H_{0.0.1}$ and $H_{0.0.2}$ are both rejected at 0.025 level, then $\alpha_{0.3} = 1/5 \times 0.025 + 1/5 \times 0.025 = 0.01$.
- Four-fifth of the remaining alpha will be transferred for testing the superiority of the key secondary endpoints for empagliflozin 10 and 25 mg. Additionally, if $H_{0.0.3}$ is rejected, the alpha $\alpha_{0.3}$ of the testing of $H_{0.0.3}$ will be equally split and added to the alpha level for testing the superiority of the key secondary endpoints. For further details, see Step 2 in Table 7.2: 1. The null hypotheses for the key secondary endpoints are as follows:

Page 76 of 122

Proprietary confidential information © 2016 Boehringer Ingelheim International GmbH or one or more of its affiliated companies

 $H_{0,1,1}$: Mean change from baseline in body weight (kg) after 26 weeks in the empagliflozin 10 mg group = Mean change from baseline in body weight (kg) after 26 weeks in the placebo group

 $H_{0,2,1}$: Mean change from baseline in TDID (U/kg) after 26 weeks in the empagliflozin 10 mg group = Mean change from baseline in TDID (U/kg) after 26 weeks in the placebo group

 $H_{0,3,1}$: Incidence rate of hypoglycaemia from Week 5 to Week 26 in the empagliflozin 10 mg group = Incidence rate of hypoglycaemia from Week 5 to Week 26 in the placebo group

 $H_{0,4,1}$: Incidence rate of hypoglycaemia from Week 1 to Week 26 in the empagliflozin 10 mg group = Incidence rate of hypoglycaemia from Week 1 to Week 26 in the placebo group

 $H_{0,5,1}$: Mean change from baseline in SBP after 26 weeks in the empagliflozin 10 mg group = Mean change from baseline in SBP after 26 weeks in the placebo group

 $H_{0,6,1}$: Mean change from baseline in DBP after 26 weeks in the empagliflozin 10 mg group = Mean change from baseline in DBP after 26 weeks in the placebo group

All tests will be done two-sided.

Similarly, we note $H_{0,1,2}$ to $H_{0,6,2}$ the null hypotheses for the test of superiority of empagliflozin 25 mg versus placebo on the key secondary endpoints.

Within each dose group (empagliflozin 10 mg and 25 mg), the key secondary endpoints will be tested sequentially with an unequal alpha split. One-tenth of the alpha level for the key secondary endpoints will be used to sequentially test $H_{0,1,1}$ and $H_{0,2,1}$. Nine-tenths of the alpha level for the key secondary endpoints will be used to sequentially test $H_{0,3,1}$ and $H_{0,4,1}$ as follows.

Depending on the success of the testing of $H_{0,0,1}$ and $H_{0,0,2}$ and $H_{0,0,3}$, $H_{0,1,1}$ will be tested at the following alpha level $\alpha_{1,1}$:

- If $H_{0,0,1}$ is rejected at 0.025 level, but $H_{0,0,3}$ is not rejected then $\alpha 1, 1 = 1/10 \times (4/5 \times 0.025) = 0.002$
- If $H_{0,0,1}$ is rejected at 0.025 level, as well as $H_{0,0,3}$, then • $\alpha_{1,1} = 1/10 \times [4/5 \times (0.025) + 1/2 \times (0.005)] = 0.00225$, if $H_{0,0,2}$ is not rejected • $\alpha_{1,1} = 1/10 \times [4/5 \times (0.025) + 1/2 \times (0.01)] = 0.0025$, if $H_{0,0,2}$ is rejected at 0.025
- If $H_{0,0,2}$ is rejected at 0.025 level, as well as $H_{0,0,3}$, but $H_{0,0,1}$ is not rejected then $\alpha_{1,1} = 1/10 \times [4/5 \times (0) + 1/2 \times (0.005)] = 0.00025$
- Otherwise $H_{0,1,1}$ will not be tested

The same will apply for $H_{0,2,1}$, provided $H_{0,1,1}$ is rejected.

Proprietary confidential information © 2016 Boehringer Ingelheim International GmbH or one or more of its affiliated companies

Depending on the success of the testing of $H_{0,0,1}$ and $H_{0,0,2}$ and $H_{0,0,3}$, $H_{0,3,1}$ will be tested at the following alpha level $\alpha_{3,1}$:

- If $H_{0,0,1}$ is rejected at 0.025 level, but $H_{0,0,3}$ is not rejected then $\alpha 3, 1 = 9/10 \times (4/5 \times 0.025) = 0.018$
- If $H_{0,0,1}$ is rejected at 0.025 level, as well as $H_{0,0,3}$, then • $\alpha_{3,1} = 9/10 \times [4/5 \times (0.025) + 1/2 \times (0.005)] = 0.02025$, if $H_{0,0,2}$ is not rejected • $\alpha_{3,1} = 9/10 \times [4/5 \times (0.025) + 1/2 \times (0.01)] = 0.0225$, if $H_{0,0,2}$ is rejected at 0.025
- If $H_{0,0,2}$ is rejected at 0.025 level, as well as $H_{0,0,3}$, but $H_{0,0,1}$ is not rejected then 0 $\alpha 3$, $1 = 9/10 \times [4/5 \times (0) + 1/2 \times (0.005)] = 0.00225$
- Otherwise $H_{0.3.1}$ will not be tested

The same will apply for $H_{0.4.1}$, provided $H_{0.3.1}$ is rejected.

Depending on the success of each sequential testing, the alpha will contribute towards the significance level for the sequential testing of $H_{0.5,1}$ and $H_{0.6,1}$.

- If $H_{0,1,1}$ and $H_{0,1,2}$ are rejected, but $H_{0,3,1}$ or $H_{0,4,1}$ are not rejected then $\alpha = \alpha_{1,1}$ will contribute towards the testing of $H_{0,5,1}$, and $H_{0,6,1}$.
- If $H_{0,3,1}$ and $H_{0,4,1}$ are both rejected, but $H_{0,1,1}$, or $H_{0,1,2}$ are not rejected then $\alpha = \alpha_{3,1}$ will contribute towards the testing of $H_{0,5,1}$, and $H_{0,6,1}$.
- If all null hypotheses $(H_{0,1,1} \text{ to } H_{0,4,1})$ are rejected, $H_{0,5,1}$ and $H_{0,6,1}$ will be tested at the level $\alpha = \alpha_{1,1} + \alpha_{3,1}$

The same approach will apply for the testing of key secondary endpoints for Empagliflozin 25 mg.

[figure not shown]
If at any stage a null hypothesis cannot be rejected, all subsequent tests in the same branch according to the diagram in Table 7.2: 1 will be performed in an exploratory manner only.

Table 7.2: 1 Summary of endpoint testing strategy

	Empagliflozin 10 mg	Empagliflozin 2.5 mg	Empagliflozin 25 mg
Step 1: Primary endpoint (efficacy) Bonferroni, two-sided (alpha=0.025)	If H _{0,0,1} for primary endpoint is rejected at alpha=0.025 level using on-treatment data only then go to step 2, otherwise procedure is stopped and subsequent tests will be done only for exploratory purposes.		If H _{0,0,2} for primary endpoint is rejected at alpha=0.025 level using on-treatment data only then go to step 2, otherwise procedure is stopped and subsequent tests will be done only for exploratory purposes.
Step 2: Primary endpoint (effectiveness)	If H _{0,0,1} is rejected at alpha=0.025 level using all on- and off-treatment data then go to step 3, otherwise procedure is stopped and subsequent tests will be done only for exploratory purposes		If H _{0,02} is rejected at alpha=0.025 level using all on- and off-treatment data then go to step 3, otherwise procedure is stopped and subsequent tests will be done only for exploratory purposes
Step 3: Primary endpoint Gatekeeping	Key secondary endpoints	H _{0,0,3} : "HbA1c" α _{0,3} 1/2 Key	4/5 secondary endpoints
	sequential testing $0 \le \alpha_{i,1} \le 0.025$ depending on previous tes		sequential testing $0 \le lpha_{i,2} \le 0.025$ ading on previous tests

Proprietary confidential information © 2016 Boehringer Ingelheim International GmbH or one or more of its affiliated companies

Table 7.2: 1 Summary of endpoint testing strategy (continued)

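### Protocol Section 7.2 has two current rules for a higher dose that fails HbA1c while the other higher dose and 2.5 mg succeed: the text passes it 0.0025 of confirmatory alpha, while Steps 1 and 2 of Table 7.2:1 make its later tests exploratory

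*Protocol*

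**What the plan says.** H0,0,1, H0,0,2 and H0,0,3 are the HbA1c nulls for 10 mg, 25 mg and 2.5 mg. Under protocol Sections 7.1 and 7.2, 10 mg and 25 mg are each tested at 0.025, first for efficacy and then for effectiveness. A dose that succeeds passes 1/5 of its alpha to the 2.5 mg test and 4/5 to its own key secondary endpoints.

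If 2.5 mg then succeeds, Section 7.1 says that "alpha of this test will be equally split and added to the alpha level for the" key secondary tests of both higher doses. Section 7.2 repeats that this alpha "will be equally split and added to the alpha level for testing the superiority of the key secondary endpoints". Neither sentence requires the receiving dose to have passed its own HbA1c test.

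The bulleted levels in Section 7.2 cover the failed-dose case explicitly, once for weight and once for hypoglycaemia: "If $H_{0,0,2}$ is rejected at 0.025 level, as well as $H_{0,0,3}$, but $H_{0,0,1}$ is not rejected then" the 10 mg levels are 0.00025 and 0.00225, with the dose's own 4/5 share multiplied by zero. Total daily insulin dose follows weight, the Week 1 to 26 rate follows the Week 5 to 26 rate, and a completed pair releases alpha to systolic and then diastolic pressure. The same approach is applied to 25 mg.

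Table 7.2:1 reads differently. In the 10 mg and 25 mg columns, Steps 1 and 2 each say that if the HbA1c null is not rejected, "otherwise procedure is stopped and subsequent tests will be done only for exploratory purposes". The sentence above the table says: "If at any stage a null hypothesis cannot be rejected, all subsequent tests in the same branch", as drawn in the diagram, become exploratory. Step 3 still shows a weight of 1/2 leaving the 2.5 mg test.

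Section 7.3 says the key secondary strategy holds type I error at 0.025 inside each dose. SAP Section 7.4.1 gives the efficacy-then-effectiveness order; the readable SAP gives no alpha levels for the key secondary endpoints.

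**The concern.** Take a trial in which 25 mg and 2.5 mg succeed on HbA1c and 10 mg does not. Under the Section 7.2 bullets, a 10 mg hypoglycaemia result with p = 0.001 is a confirmatory finding. Under Steps 1 and 2 of the table, the same result is exploratory. Both texts are current and neither refers to the other as an exception.

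What is at stake is which dose may carry a confirmatory claim on weight, insulin dose, hypoglycaemia or blood pressure. That should be settled by one rule before the results are seen. There is also a knock-on effect: if the bullets govern, the per-dose error statement in Section 7.3 needs correcting.

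**Working it through.** **Inputs.** Alpha of 0.025 per higher dose (Section 7.1). Weights of 1/5 and 4/5 after HbA1c success, 1/2 from 2.5 mg to each higher dose, and 1/10 and 9/10 within a dose's key secondary family (Section 7.2). Difference 0.3, SD 0.9 and 225 per arm (Section 7.7).

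**1. The plan's own levels.** Let R = 1 if a dose's HbA1c null is rejected and 0 otherwise.

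- Level for 2.5 mg: α0.3 = 1/5 × 0.025 × (R10 + R25) = 0.005 × (R10 + R25)
- 10 mg family: A10 = 4/5 × 0.025 × R10 + 1/2 × α0.3 × R2.5
- Weight, then insulin dose: α1,1 = A10/10. Hypoglycaemia rates: α3,1 = 9 × A10/10

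| 10 mg | 25 mg | 2.5 mg | A10 | α1,1 | α3,1 |
|---|---|---|---|---|---|
| pass | fail | fail | 0.020 | 0.002 | 0.018 |
| pass | pass | fail | 0.020 | 0.002 | 0.018 |
| pass | fail | pass | 0.0225 | 0.00225 | 0.02025 |
| pass | pass | pass | 0.025 | 0.0025 | 0.0225 |
| fail | pass | pass | 0.0025 | 0.00025 | 0.00225 |

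All ten levels agree with Section 7.2. The last row is the case at issue: 4/5 × 0.025 × 0 + 1/2 × 0.005 = 0.0025. Blood pressure can then be reached at up to 0.00025 + 0.00225 = 0.0025. Under Steps 1 and 2 of Table 7.2:1, A10 in that row is 0.

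**2. Error bounds in that case.** Suppose the 10 mg nulls and the 25 mg key secondary nulls are true, and 25 mg and 2.5 mg succeed on HbA1c. The 25 mg family then has 4/5 × 0.025 + 1/2 × 0.005 = 0.0225.

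| | Section 7.2 bullets | Table Steps 1–2 |
|---|---|---|
| Within 10 mg (HbA1c and key secondary together) | 0.025 + 0.0025 = 0.0275 | 0.025 |
| Overall | 0.025 + 0.0025 + 0.0225 = 0.05 | 0.025 + 0.0225 = 0.0475 |

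A simulation agreed with these bounds. It took 25 mg and 2.5 mg as always rejected on HbA1c, used one weight and one hypoglycaemia test per dose, treated endpoints as independent, and set the correlation between doses on the same endpoint at 0.5. Within-dose error was 0.0275 (bullets) and 0.0251 (table); overall error was 0.049 and 0.047.

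**3. How often the case arises.** Two-sample t-test power at 225 per arm is 90.0%, 82.8% and 76.2% at alpha 0.025, 0.01 and 0.005. Section 7.7 states 90%, 82% and 76%. If the two higher-dose tests were independent, exactly one would fail with probability 2 × 0.90 × 0.10 = 0.18. The shared placebo arm makes them positively correlated and lowers this. Simulating four arms with a shared placebo (2 million trials, true effect 0.3 in every dose):

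- 10 mg fails and 25 mg passes: about 0.067, and the same for the mirror case, so about 0.13 that exactly one fails
- exactly one fails and 2.5 mg passes at 0.005: about 0.067

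The effectiveness step is not modelled.

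**The case against.** The strongest reply is that this is ordinary alpha recycling, correctly specified, and that Table 7.2:1 is only a summary of it. Much supports that. Sections 7.1 and 7.2 both send the 2.5 mg alpha to the two higher doses without condition. The bullets name the failed-dose case twice and write out a zero for the dose's own share, which is hardly a slip. Step 3 of the table carries the 1/2 weight. The stop sentence is limited to one branch of the diagram, so alpha arriving from the 2.5 mg test could count as a different branch. I accept that this is probably the intent.

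It does not remove the conflict. The Step 1 and Step 2 cells stop the dose's procedure and all its later tests, with no exception for alpha arriving from elsewhere. The recycling reading also leaves Section 7.3 inaccurate if its 0.025 covers the dose's HbA1c and key secondary tests together.

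A reader might go further in three ways that the documents do not support:

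- **That overall type I error is inflated.** It is not; the bound under the bullets is 0.05.
- **That the plan leaves the levels open to choice after unblinding.** Exact levels are prespecified for this case. The defect is a second rule that contradicts them.
- **That a dose failing HbA1c must not be tested further, because insulin changes cloud its hypoglycaemia result.** Insulin adjustment is allowed in every arm (protocol Section 4.2.1), so that argument is not specific to a failed dose, and the gatekeeping design is valid.

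**Conclusion.** The point stands as an inconsistency in the decision rule. For a higher dose that fails HbA1c when the other higher dose and 2.5 mg succeed, the Section 7.2 text gives 0.0025 of confirmatory alpha and Steps 1 and 2 of Table 7.2:1 give none. The first rule puts the failed dose's own bound at 0.0275, against 0.025 in Section 7.3.

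The practical size is modest. The case arises in about 7% of trials if every dose truly lowers HbA1c by 0.3 with SD 0.9 and 225 per arm, leaving out the effectiveness step. That 7% should not be read as the chance of a disputed claim: such a claim also needs a key secondary p-value below 0.00225 or 0.00025, which was not modelled. Nor are all six endpoints open at once; they are reachable only in sequence.

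The arithmetic is certain. Confidence that the two rules truly conflict is medium, because the diagram that defines the branches was not fully legible in the text reviewed.

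**What to change.** Choose one rule before unblinding and align Sections 7.1, 7.2 (bullets and Table 7.2:1) and 7.3 with it, by protocol or SAP wording.

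**(a) Keep the transfer.** State in Steps 1 and 2 that the stop applies only to that dose's own alpha, meaning its 4/5 share and its 1/5 contribution to the 2.5 mg test. Correct Section 7.3 to say that error is controlled at 0.05 overall, with a within-dose bound of 0.0275. This fits most of the existing text and costs only wording.

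**(b) Remove the transfer to a failed dose.** Delete the two failed-dose bullets and their 25 mg mirror. Make the transfer in Sections 7.1 and 7.2 and the Step 3 weight conditional on the receiving dose having passed both HbA1c steps. Deleting the bullets alone is not enough, because those other places would still send alpha to both doses. Also say what happens to the freed 0.0025. Left unused, the overall bound in this case is 0.0475; given to the surviving dose, that dose's family rises to 0.0225 + 0.0025 = 0.025 and the overall bound returns to 0.05. The cost is the loss of confirmatory tests at 0.00025 and 0.00225 for the failed dose.

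The choice is the sponsor's. Two slips in Section 7.2 can be corrected in the same edit: the pointer to Step 2 of the table for the alpha split, which is in Step 3, and the use of H0,1,2 in the 10 mg blood pressure bullets where the sequence calls for H0,2,1.

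### The 10 mg rule that releases alpha to SBP and DBP names 25 mg weight (H0,1,2) where the sequence needs 10 mg TDID (H0,2,1)

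*Protocol*

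**What the plan says.** Protocol Section 7.2 gives each key secondary null hypothesis a last index for dose. Index 1 is 10 mg: H0,1,1 weight, H0,2,1 TDID, H0,3,1 and H0,4,1 hypoglycaemia (Weeks 5–26 and 1–26), H0,5,1 SBP and H0,6,1 DBP. Index 2 is 25 mg: "Similarly, we note $H_{0,1,2}$ to $H_{0,6,2}$ the null hypotheses for the test of superiority of empagliflozin 25 mg versus placebo". H0,1,2 is therefore 25 mg weight.

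Within 10 mg, one-tenth of the key secondary alpha (α1,1) goes to weight and then TDID: "The same will apply for $H_{0,2,1}$, provided $H_{0,1,1}$ is rejected". Nine-tenths (α3,1) goes to the two hypoglycaemia tests in order. Release to SBP and DBP is introduced by "Depending on the success of each sequential testing, the alpha will contribute towards the significance level for the sequential testing of" H0,5,1 and H0,6,1. Three bullets follow:

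- First: "If $H_{0,1,1}$ and $H_{0,1,2}$ are rejected, but $H_{0,3,1}$ or $H_{0,4,1}$ are not rejected then $\alpha = \alpha_{1,1}$ will contribute towards the testing of" H0,5,1 and H0,6,1.
- Second: "If $H_{0,3,1}$ and $H_{0,4,1}$ are both rejected, but $H_{0,1,1}$, or $H_{0,1,2}$ are not rejected then $\alpha = \alpha_{3,1}$ will contribute" to the same tests.
- Third: if H0,1,1 to H0,4,1 are all rejected, SBP and DBP are tested at α1,1 + α3,1.

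For the higher dose the protocol adds only "The same approach will apply for the testing of key secondary endpoints for Empagliflozin 25 mg". A stop rule then makes later tests in the same branch exploratory after a non-rejection, with branches as drawn in Table 7.2: 1.

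SAP Section 3 bases the analysis on protocol Section 7. The visible text of SAP Section 4 (changes to the planned analysis) and Section 7.5.1.4 (blood pressure) neither restates nor corrects the release rule.

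**The concern.** The first two bullets bring a 25 mg hypothesis into a 10 mg rule and leave out 10 mg TDID, the second test in the chain whose alpha is being released. Programmed as printed, the level for 10 mg SBP and DBP would depend on whether 25 mg weight was rejected. Alpha earned at 10 mg could be withheld, and alpha already spent on a failed TDID test could be released again. The 25 mg rule is not written out, so the slip could be copied there. If the wording is left as it is, someone must choose a reading after the results are known.

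**Working it through.** **Stated levels.** The levels that feed the bullets reproduce. With all three HbA1c nulls rejected:

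- α1,1 = 1/10 × [4/5 × 0.025 + 1/2 × 0.01] = 0.0025
- α3,1 = 9/10 × [4/5 × 0.025 + 1/2 × 0.01] = 0.0225

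The levels for the other HbA1c outcomes also reproduce. The fault lies in the condition for release, not in the levels.

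**Enumeration.** Weight–TDID at 10 mg has 3 states (weight not rejected; weight only; both). Hypoglycaemia at 10 mg has 3 states in the same way. 25 mg weight is rejected or not. That makes 3 × 3 × 2 = 18 reachable outcomes. The printed bullets were compared with the same bullets using H0,2,1:

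| Case | Outcomes | Pattern | Printed | Intended |
|---|---|---|---|---|
| a | 2 | 10 mg weight and TDID rejected; hypoglycaemia chain incomplete; 25 mg weight not rejected | none | α1,1 |
| b | 1 | weight rejected at both doses; TDID not; both hypoglycaemia nulls rejected | none | α3,1 |
| c | 1 | all four 10 mg nulls rejected; 25 mg weight not rejected | bullets 2 and 3 both apply (0.0225 or 0.025) | 0.025 |
| d | 2 | weight rejected at both doses; TDID not; hypoglycaemia chain incomplete | α1,1 | none |

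The rules differ in 2 + 1 + 1 + 2 = 6 of 18 outcomes. This is a count, not a probability. With H0,2,1 inserted, the three bullets are mutually exclusive and cover every outcome in which a chain is completed.

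**Error within the 10 mg dose.** Only case (d) can add error, because α1,1 is spent on TDID and again on SBP. Take weight rejected at both doses and TDID, hypoglycaemia and SBP all null:

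- Printed, upper bound: 2 × 0.0025 + 0.0225 = 0.0275, against the 0.025 per dose in protocol Section 7.3
- Printed, independent endpoints: 1 − 0.9975² × 0.9775 = 0.0274
- Intended, independent endpoints: 1 − 0.9975 × 0.9775 = 0.0249

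In the other HbA1c scenarios the printed rule stays within 0.025. If 2.5 mg is not rejected, it gives 2 × 0.002 + 0.018 = 0.022. If only 10 mg and 2.5 mg are rejected, it gives 2 × 0.00225 + 0.02025 = 0.02475.

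**Overall error, same conditions.** Assume independent endpoints and, within each endpoint, bivariate normal statistics for the two doses with correlation r. Neither assumption is in the documents; r = 0.5 is the value for a shared placebo at equal allocation. Let A and B be the probabilities that neither dose is rejected at 0.0025 and at 0.0225. The error is 1 − AB (intended), 1 − AB × 0.9975 (misprint at 10 mg only) and 1 − A²B (misprint mirrored at 25 mg). At r = 0.5, A = 0.99515 and B = 0.95805.

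| r | Intended | 10 mg only | Mirrored |
|---|---|---|---|
| 0 | 0.0493 | 0.0516 | 0.0540 |
| 0.25 | 0.0487 | 0.0510 | 0.0534 |
| 0.5 | 0.0466 | 0.0490 | 0.0512 |
| 0.75 | 0.0420 | 0.0444 | 0.0463 |
| 0.9 | 0.0364 | 0.0388 | 0.0402 |

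The upper bounds are 0.05, 0.05 + 0.0025 = 0.0525 and 0.05 + 2 × 0.0025 = 0.055.

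**The case against.** The strongest reply is that nobody could mistake the intent. Section 7.2 keeps key secondary testing within each dose, puts H0,2,1 after H0,1,1, ties release to completing each sequence, and uses only 10 mg hypotheses in the third bullet. H0,2,1 is the only reading that fits all four. On that view this is an erratum.

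The reply can also shrink the effect. If weight and TDID form one branch, the stop rule bars case (d). In case (c) the bullets say that alpha contributes, which is compatible with the sum of 0.025. That leaves (a) and (b), three outcomes that cost power for SBP and DBP and cannot inflate error. Every inflation figure needs the bullets to override the stop rule. At r = 0.5 the misprint as printed stays under 0.05, and 0.0512 depends on 25 mg bullets that the protocol does not contain. Finally, the Table 7.2: 1 diagram is not shown in the available text, and it may give the right order and define the branches.

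Most of this stands, and it limits the point. It does not remove it. Cases (a) and (b) need no override of the stop rule: following the printed text denies alpha that the 10 mg chains earned. If the diagram is right, the text contradicts it and the two still have to be reconciled. A confirmatory alpha rule should not have to be inferred.

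**Conclusion.** The point holds. Both partial-release bullets carry the wrong index, almost certainly a transposition of H0,2,1, and nothing visible corrects it. Printed and intended rules part in 6 of 18 outcomes, and in three of these earned alpha is plainly withheld.

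Inflation is a remote, conditional matter. The 0.0275 bound needs all three HbA1c nulls rejected, weight rejected at both doses, TDID, hypoglycaemia and SBP all null, and the bullets placed above the stop rule. Otherwise 0.025 per dose holds. At r = 0.5 the overall error passes 0.05 only if the slip is repeated at 25 mg.

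The damage is confined to SBP and DBP, the last tests in the hierarchy. The levels for HbA1c, weight, TDID and hypoglycaemia do not change, nor does the sample size. The conclusion is subject to the unseen diagram and to redacted parts of the SAP. It should be fixed, but it does not threaten the primary result.

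**What to change.** - In both partial-release bullets, replace H0,1,2 by H0,2,1.
- Write out the 25 mg rule: α1,2 goes to H0,5,2 and H0,6,2 only if H0,1,2 and H0,2,2 are both rejected; α3,2 only if H0,3,2 and H0,4,2 are both rejected; the sum if all four are rejected.
- State that a failed test ends only the chain carrying its alpha (weight–TDID or hypoglycaemia). If the Table 7.2: 1 diagram already says so, a cross-reference is enough.
- Check the diagram against the corrected text.

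The cost is two index corrections and two clarifying sentences in protocol Section 7.2. SAP Section 4, where departures from the protocol are recorded, should carry the same correction. No patients or data are needed. The documents do not show whether the trial has been unblinded; the change should be made and dated before that happens.
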